**Figure 6: Correlation of cortical cholinesterase with dSAT**

**Procedures:** This experiment will be conducted in parallel with those for SA2. Attention will be evaluated with the dSAT at all evaluation points in the double-blind crossover design VCN intervention study described above. We will correlate dSAT changes in response to VCN with gait speed and postural control changes in response to VCN. The sample size is determined from the goals of **SA2**. With this sample size, an effect size of 0.4 can be detected with at least 80% power and a two-sided Type I error of 0.05 assuming a within-subject correlation of 0.69. Similar statistical methods as those used for SA2 will be employed to test the impact of VCN on dSAT. An exploratory analysis will be conducted to examine medication of treatment effects on gait and other postural outcomes by dSAT. In the presence of a treatment effect, a variable is declared a mediator if it complies with three things: it is affected by the treatment, it predicts the endpoint of interest, and the treatment effect is attenuated when the potential mediating factor is adjusted for. Mediation analysis will be conducted by including mediating factors in the mixed model regression analysis outlined above. Structural equation models will be used to estimate the direct effect of VCN and the indirect effects of the VCN due to mediators, as has been recommended for intervention studies of disease prevention (114,115).

**Potential Problems and Alternatives:** All procedures, including the dSAT, are well established in our center. Most of the potential problems are discussed above (**SA2 Potential Problems and Alternatives**). Our prediction is that improved dSAT performance will correlate with improved gait speed and postural control measures. There may be dissociations between results of dSAT testing and gait speed-postural control outcome measures. Attentional performance may improve but not gait speed and postural control. Gait speed and postural control may improve without commensurate improvements in dSAT performance. These outcomes would be important for evaluating our understanding of how cholinergic deficits degrade gait and postural control. Lack of correlation would direct future research away from attentional mechanisms and towards alternative mechanisms, such as PPN projection roles in sensorimotor integration. We will have [F]FEOBV data on cholinergic projection systems integrity for all these subjects and secondary analyses looking at specific functional deficits and specific pathway changes may be revealing. Whether or not dSAT performance response correlates with improvements in gait speed and postural control measures is also important for evaluating the validity of the dual lesion model. It is crucial to know the limitations of this interesting model prior to using it extensively for preclinical evaluations of potential therapies.

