**Hypothesis 3:** Pharmacologic  $\alpha 4\beta 2^*$  nAChR activation in PD subjects with cholinergic deficits will improve attentional performance on the SAT. The improvement in SAT performance will correlate with improvement in laboratory measures of gait function and postural control assessed in Specific Aim 2.

Our group possesses unique expertise in preclinical models, nAChR pharmacology, cholinergic imaging, and physiological measures of gait function, postural control, and attention. This project interacts directly with **Project II**, depends on the **Clinical Resource Core**, and is strongly connected to **Project I** preclinical experiments. The potential impact of the proposed experiments is considerable. This work would provide strong support for our *central hypothesis*, establish therapeutic validity of the novel animal model employed in **Project I**, and implement new methodologies for the evaluation of treatments to improve gait and balance deficits in PD. These experiments would identify  $\alpha 4\beta 2^*$  nAChRs as a therapeutic target in a clinically definable PD subgroup, setting the stage for trials of  $\alpha 4\beta 2^*$  nAChR agonists as adjunctive treatments to mitigate balance and gait abnormalities in these patients.

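### Shared visit-to-visit variation can meet the mediator rule without mediation, and at 33 patients a null correlation of changes is weak evidence against attention

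*Protocol*

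**What the plan says.** Hypothesis 3 (Protocol, Specific Aims) has two parts: VCN improves attention, and "The improvement in SAT performance will correlate with improvement in laboratory measures of gait function and postural control". The Procedures for Specific Aim 3 implement the second part: "We will correlate dSAT changes in response to VCN with gait speed and postural control changes in response to VCN". No threshold, interval or power is given for this correlation.

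The same paragraph adds a mediation analysis, labelled exploratory: "An exploratory analysis will be conducted to examine medication of treatment effects on gait and other postural outcomes by dSAT" (the fourth-last idea in that sentence is evidently mediation). The rule applies only where VCN has an effect, and then "a variable is declared a mediator if it complies with three things". Its conditions, as written, are that "it is affected by the treatment, it predicts the endpoint of interest, and the treatment effect is attenuated when the potential mediating factor is adjusted". On fitting: "Mediation analysis will be conducted by including mediating factors in the mixed model regression analysis outlined above". Structural equation models for direct and indirect effects are planned as well.

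Under Potential Problems and Alternatives for the same aim, the reading of a null is given in advance: "Lack of correlation would direct future research away from attentional mechanisms". The correlation is also to inform the validity of the rodent model.

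The SAP does not add to this. Its objective (section 3.1) is receptor occupancy, and section 4.1 refers to the crossover as a future study.

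**The concern.** VCN is randomized in the crossover; dSAT is not. Anything that moves attention and gait together at a visit, such as fatigue, creates a within-patient association between them. Adding dSAT to the gait model then removes part of the VCN effect even if VCN reaches gait by another route. The rule sets no minimum attenuation, and no assumption of no dSAT-gait confounding is stated. The structural equation model depends on the same unstated assumption.

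The correlation raises a different problem. Its absence is to count against the attentional mechanism, but the only power figure for Aim 3 concerns the mean effect on dSAT. A null could come from too few patients, and an apparent correlation could come from shared visit noise. At stake is what the trial may conclude about mechanism and about the rodent model, not the primary comparison or safety.

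**Working it through.** **Inputs from the protocol.** Aim 3 Procedures: dSAT effect 0.4, two-sided 5%, within-subject correlation 0.69. Aim 2 Sample Size: 33 patients, gait effect 0.112 m/s, Bonferroni-adjusted two-sided 2.5%, within-subject correlation 0.64, power 80%; enrolment 42. Aim 2 and Aim 3 Procedures: gait and dSAT assessed at the same four points.

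**Not stated in the protocol.** The gait SD is back-solved from the Aim 2 power statement (noncentral t), giving 0.236 m/s. The visit-error correlation between dSAT and gait is assumed, and shown at 0, 0.2 and 0.3.

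**1. The plan's own figure.** Standardized VCN-minus-placebo difference for dSAT: 0.4/√(2(1−0.69)) = 0.508. With 33 patients, two-sided 5%, power is 80.8%. The stated 80% reproduces, but only for the mean dSAT effect.

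**2. Mediator rule with no mediation.** For gait: 0.112/(0.236 × √(2(1−0.64))) = 0.559. If VCN acts on gait only directly, every patient responds alike and visit errors correlate at r, the two differences correlate at r. The share of the gait effect that adjustment removes is r × 0.508/0.559: 18% at r = 0.2 and 27% at r = 0.3.

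The adjusted effect is the total effect minus slope × dSAT effect. Once dSAT improves and predicts gait with a positive slope, attenuation follows, so the third condition adds almost nothing. Taking *predicts* as a significant positive association at two-sided 5% (the protocol gives no criterion), the chance of meeting the rule is roughly the product of three probabilities:

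| Visit-error correlation | Gait effect found | dSAT effect found | Association found | Rule met |
|---|---|---|---|---|
| 0 | 0.80 | 0.81 | 0.025 | about 2% |
| 0.2 | 0.80 | 0.81 | 0.20 | about 13% |
| 0.3 | 0.80 | 0.81 | 0.40 | about 26% |

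Simulation of the paired differences at 33 patients gives the same results.

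**3. Correlation of changes.** By Fisher's z, the 95% limits around an observed r of 0 are ±tanh(1.96/√(n−3)), and power is approximately Φ(atanh(r) × √(n−3) − 1.96).

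| n | 95% CI at r = 0 | Power at r = 0.2 | r = 0.3 | r = 0.4 |
|---|---|---|---|---|
| 33 | ±0.34 | 20% | 40% | 64% |
| 42 (no dropout) | ±0.30 | 24% | 49% | 75% |

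At 33 patients, 80% power needs a true r of tanh((1.96 + 0.84)/√30), about 0.47. A true r of 0.3 would need 85 patients.

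**The case against.** Much of the case for leaving this alone is sound. The mediation analysis is labelled exploratory in a pilot study. An indirect effect from structural equation models is already planned. The crossover removes stable patient differences when the comparison is within patient, and dopaminergic treatment is held stable, which limits one source of shared variation. The sentence about future research is conditional, sits in a discussion of possible problems and sets no threshold; the same paragraph anticipates dissociations and plans pathway analyses.

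Three stronger readings are tempting and are not supported.

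- **That a null correlation is the likely result.** This requires visit noise shared between dSAT and gait to be absent, which contradicts the assumption behind the false-positive risk. Take visit-error correlation e = 0.2–0.3, response SD h = 0.2–0.6 in both measures and response correlation 0.61, all assumed (0.61 is borrowed from the rodent SAT-fall correlation in the Preclinical Data, which is not a correlation of responses). Expected r = (0.61h² + e√(0.62 × 0.72))/√((h² + 0.62)(h² + 0.72)), or 0.22 to 0.41, with power 24% to 66%.
- **That full mediation with a uniform benefit leaves changes uncorrelated.** This holds only if no visit-to-visit dSAT variation reaches gait. The protocol's effects imply a gait gain per unit of dSAT of (0.112/0.236)/0.4 = 1.19 in SD units. If half the within-patient dSAT variance is real attention (assumed), r = 1.19 × 0.31/√(0.62 × 0.72), about 0.55, with power about 92%. At a quarter, r is about 0.28.
- **That the protocol commits to redirecting research.** It states an interpretation, not a decision rule.

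What stands is narrower. The declaration rule remains beside the structural equation model, which needs the same no-confounding assumption. The correlation belongs to Hypothesis 3 and is not labelled exploratory, and the planned reading of its absence has no interval behind it.

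**Conclusion.** The point holds in limited form and is minor. Neither analysis, as written, can carry the conclusion attached to it. The mediator rule can be met without mediation in roughly one trial in eight to one in four if visit errors correlate at 0.2 to 0.3. These percentages rest on that assumed range, the back-solved gait SD, a uniform response and a 5% criterion for prediction; the documents give no estimate of the visit-error correlation.

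The sample-size result needs fewer assumptions: with 33 patients a correlation of zero is compatible with true values up to about 0.34, so its absence is weak evidence against attention. Shared visit noise can also push the correlation upward, so a positive result is not clean evidence either. The documents do not show which error is more likely.

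**What to change.** In the Aim 3 Procedures, remove the three-condition declaration and rest on the indirect effect already planned. Report it with a bootstrap CI, state the no-confounding assumption, and add a sensitivity analysis over a range of residual dSAT-gait correlations.

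Report the correlation of changes with its CI. Fit a bivariate mixed model to all four visits, with period terms, to separate visit-level residual correlation from correlation of responses where this can be estimated. With one VCN assessment per patient, the separation assumes similar residual variation on and off drug, and this should be said.

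In Potential Problems and Alternatives, state that a null correlation is inconclusive unless its CI excludes a value fixed in advance, and apply the same reading to the rodent-model inference.

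No new patients or data are needed. The cost is one extra model, some wording, and a weaker stated conclusion.

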### **Standard Methods:**

**MRI and VMAT2 PET Imaging, Standard PET Methods and Image Processing:** See **Clinical Resource Core**. **Flubatine PET Imaging:** [18F]Flubatine will be prepared in high radiochemical purity (>95%) with a method developed by our group (68). PET scans will be acquired using a protocol consisting of 18 frames acquired over 90 min following bolus injections of 8 mCi [F]flubatine. Individual image frames within each scan will be co-registered to frame 10 (10-15 min post-injection) to account for patient motion. Full kinetic modeling requires arterial blood sampling and >two hours of imaging, impractical for this patient population and we will use simpler analyses. Our primary analysis will use an average of the 70-90 min scan data, when tissue TACs are relatively constant, approaching equilibrium (Figure 3). Venous blood samples will be drawn at 70 and 90 min, plasma extracted and counted in a NaI well-counter. Plasma metabolites will be assessed to determine the radioactivity concentration of authentic flubatine. Radiotracer binding measures will be obtained by normalizing the PET tissue concentrations to the authentic venous plasma radiotracer concentration averaged over the 70 and 90 min samples. This measure of tracer binding approximates the total tissue volume of distribution relative to plasma,  $V_T$ . This method is well suited to quantification of flubatine binding as flubatine undergoes minimal catabolism, has only moderate plasma protein binding, and equilibrates instantaneously between blood and plasma (116). A secondary analysis will use the simplified reference tissue model (sRTM) (117). SRTM assumes a reference tissue devoid of specific binding sites, used in lieu of an arterial plasma input function to estimate tissue binding potentials. Since no gray matter tissue is devoid of specific binding sites for flubatine, we will test white matter as a reference tissue. White matter reference regions will be defined on co-registered MR volumes, and segmented with FreeSurfer to produce white matter masks. Binary masks, smoothed to PET resolution with white matter defined by all brain voxels with a mask value >0.9 after smoothing, will assure that reference region voxels have >90% contribution from white matter.

**Gait Speed and Postural Control Methods:** Gait and postural control will be assessed in the Functional Neuroimaging, Cognitive and Mobility Laboratory with Mobility Lab (APDM, Portland, OR) systems now standard in our center (see **Project II, SA2 Preliminary Data**). The postural control and gait assessments are usually completed in approximately 45 minutes. These studies will be performed in the **Clinical Resource Core** using methodology described in detail in **Project II**.

**dSAT:** The dSAT will be administered as described previously (108-110). A PC with E-Prime software is used to present either a visual signal or no cue in the middle of the screen followed after a constant delay by an auditory signal to indicate via key pushing whether or not a visual signal was presented. Using different keys, participants indicate both signal presentation and non-presentations. Participants receive feedback on response accuracy with a small financial reward for correct responses on each trial. Signal durations and inter-trial intervals are varied. In the distractor condition, the background screen alternates between silver and black at 10 Hz. This task requires minimal training and reliable data is obtained in a single session. The SAT score is calculated from all outcomes.

**Future Directions:** These experiments are likely to lead in several useful directions. Demonstration that  $\alpha 4\beta 2^*$  nAChR stimulation improves physiological measures of gait function and postural control in hypocholinergic PD subjects will spur investigation of  $\alpha 4\beta 2^*$  nAChR agonists for treatment of gait and postural control problems in PD. nAChR pharmacology is an active area of industrial R&D with compounds going to phase II trials and coming to market. With the preclinical methods exemplified by the novel model featured in **Project I** and methods used in this project, we would be well positioned to evaluate other  $\alpha 4\beta 2^*$  nAChR agonists or other cholinergic agents as adjunctive treatments in PD. We would aggressively evaluate additional promising compounds. Our group would move an  $\alpha 4\beta 2^*$  nAChR agonist into clinical trials for PD, preferably in phase IIa trials. The development and validation of convenient methods to identify the subset of PD patients with cholinergic deficits (see **Project II** and **Clinical Resource Core**), and the relatively non-invasive physiologic methods used to evaluate  $\alpha 4\beta 2^*$  nAChR stimulation in this study would be valuable components of such studies. Our group, with large clinic populations, strong clinical expertise, an institutional CTSA (Michigan Institute for Clinical & Health Research; MICHR), and strong expertise in both the basic and clinical pharmacology of cholinergic agents would be well positioned to lead the development of novel cholinergic therapies for PD. We would pursue these studies outside the Udall Center mechanism with complementary R01, U01, translational R21, or NeuroNext applications.

## **Project III: Protection of Human Subjects**

### **i) Human Subjects**

Description of subject populations: Subjects will include 57 PD subjects and 12 control subjects.

Recruitment: Subjects will be recruited from the UMHS and VAAAHS Movement Disorders Clinics, the **Clinical Resource Core** and with the assistance of the **Education and Outreach Core**. The UMHS Movement Disorders clinic follows a population of approximately 2,000 clinically well-defined patients with PD and/or parkinsonism and will be the main source of recruitment of patients for this study. [name], Co-Director of the UMHS Movement Disorders Clinic, will be in charge of UM patient recruitment. In addition, subjects will be recruited from the VAAAHS Movement Disorders clinic, directed by [name], and currently follows approximately 250 well-defined subjects with PD. At present, we recruit 4-6 subjects with PD for imaging studies at UM per month. We anticipate that about some participants for this study can be recruited from the concluding P01 NS15655 ([name], PI) that studied about 4 subjects with PD per month, most of whom have longer duration of disease. Further information about recruitment and retention are described in the **Clinical Resource Core** and the **Education and Outreach Core**.

#### Inclusion Criteria:

1. PD diagnosis will be based on the United Kingdom Parkinson's Disease Society Brain Bank Research Center (UKPDSBRC) clinical diagnostic criteria. We will enrich the cohort using the following strategies: recruiting subjects at modified Hoehn and Yahr stages 2 or higher (from data collected in a medication "OFF" state in UDALL project 2), recruiting subjects with a duration of motor disease 5 years or longer, recruiting subjects that are age >65 years, or recruiting subjects with the PIGD phenotype. Duration of motor disease will be defined as the time between onset of motor symptoms and time of entry into the study. The PIGD phenotype is defined as described previously. PD subjects with defined cholinergic deficits will be recruited as described in **Project II**. PD subjects will have cortical cholinergic deficits based on 5th percentile cutoff of the normal controls as defined previously.
2. PD Patients with stable dopaminergic replacement therapy for 3 months prior to enrollment and expected to maintain stable dopaminergic therapy for duration of study participation.

## **OR**

3. Normal healthy control individuals age 45 years and older without any history of neurological disease.

**Exclusion Criteria:**

1. Other disorders which may resemble PD with or without dementia, such as vascular dementia, normal pressure hydrocephalus, progressive supranuclear palsy, multiple system atrophy, corticobasal ganglionic degeneration, or toxic causes of parkinsonism. Prototypical cases have distinctive clinical profiles, like vertical supranuclear gaze palsy, early and severe dysautonomia or appendicular apraxia, which may differentiate them from idiopathic PD. The use of the UKPDSBRC clinical diagnostic criteria for PD will mitigate the inclusion of subjects with atypical parkinsonism and all participants will undergo [C]DTBZ PET to confirm striatal dopaminergic denervation.
2. Subjects on neuroleptic, anticholinergic (trihexiphenidyl, benztrapine), or cholinesterase inhibitor drugs.
3. Current or previous (within last 6 months) use of any product or medication containing nicotinic agents, including use of tobacco products such as cigarettes, cigars, pipes, chewing tobacco, etc., e-cigarettes, OTC nicotine patches, chewing gum containing nicotine, or varenicline.
4. Evidence of a stroke or mass lesion on structural brain imaging (MRI).
5. Participants in whom magnetic resonance imaging (MRI) is contraindicated including, but not limited to, those with a pacemaker, presence of metallic fragments near the eyes or spinal cord, or cochlear implant.
6. Severe claustrophobia precluding MR or PET imaging
7. Subjects limited by participation in research procedures involving ionizing radiation.
8. Pregnancy (test within 48 hours of each PET session) or breastfeeding.
9. Significant risk of cardiovascular event.
10. Active, significant mood disorder.
11. History of seizures.
12. Active alcohol abuse.

**ii) Sources of Materials**

Information gathered specifically for this research project includes test results from clinical test scales, standardized neuropsychological measures and from experimental cognitive tests, neurobehavioral rating scales, clinical motor data, questionnaires, standardized interview, and data derived from the PET studies that reflect the amount of dopaminergic nerve terminals, cholinergic nerve terminals, and nicotinic receptors in the brain, and from structural MRI.

**iii) Potential Risks**

Confidentiality of Research Information: The research data to be collected from subjects will consist of confidential information relating to clinical, neuropsychological, mood, partial genotype, neuroanatomical, and neurochemical functions. These research data are not intended for entry into the subjects' clinical medical records. However, the data remain potentially discoverable. This may lead to violation of privacy and embarrassment of subjects.

Clinical, neuropsychological and Behavioral Testing: Risks in regard to the neuropsychological, behavioral, and motor assessments are limited to fatigue, frustration and momentary embarrassment that may occur when one experiences difficulty performing a task or learning a new skill.

PET scans & Venipuncture: Insertion of a catheter for intravenous injection of the PET radiopharmaceutical may be commonly associated with slight pain or bruising at the puncture site and rare chance of infection. Participation in this research study will involve exposure to radiation associated with the PET transmission scans and the administration of the radioactive drugs. Subjects participating in experiments involving PET imaging will undergo 2 [F]Flubatine PET studies. These subjects will have previously undergone [C]DTBZ and [F]FEOBV PET and in some subjects undergoing [F]Flubatine PET may be studied in the same year as they undergo DTBZ and FEOBV PET, for a total of 4 PET studies in 1 year. Maximum total dosimetry for any subject would be 15 mCi for DTBZ, and 8 mCi for each FEOBV and flubatine study. Total exposure will be well below the annual radiation exposure (5 rem) permitted to radiation workers by federal regulations. Participants will be instructed to void two hours post injection to minimize bladder exposure. This radiation dose is not expected to produce any harmful effects, although there is no known minimum level of radiation exposure for non-radiation workers considered to be totally free of the risk of causing genetic defects or cancer. The risk associated with the amount of radiation exposure participants receive in this study is considered low and comparable to every day risks. In the event of incomplete imaging or technical failure, it may be necessary to repeat the [F]Flubatine

PET scan. We will not exceed radiation dose limits. No PET studies will be performed on pregnant or potentially pregnant women, as confirmed by pregnancy testing. The use of these PET tracers is considered to be generally safe and effective as approved by the University of Michigan Radioactive Drug Research Committee in accordance with Food and Drug Administration regulations (21 CFR 361.1). Adverse reactions to tracers used in this study have not been reported. However, the possibility exists for a rare reaction to any of the drugs or procedures to which the participant will be exposed. ACLS-certified staff will be in attendance at all times during the study and an emergency cart will be in close proximity. Other physical risks involve possible muscle aches from lying still. Medical intervention will be furnished by UMHS if serious adverse effects would occur.

Participants will be asked to provide a blood sample on two separate visits. There is an infrequent risk of bruising, bleeding, infection or soreness associated with the venipuncture, similar to the risks associated with routine blood testing. Participants may feel dizzy or lightheaded or may rarely even faint when the needle is put in or taken out.

**Mood Disorder:** In anecdotal reports, VCN has been associated with increased risk of significant mood disorder, including worsening mood, suicidal ideation, suicide attempts, and completed suicide. The FDA issued a "Black Box" warning for VCN because of concerns about these possible psychiatric side-effects of VCN. Though present data do not substantiate a connection between VCN administration and serious mood problems (see **Approach**), we will exclude patients with active mood disorders.

**Cardiovascular Risk:** In anecdotal reports, VCN has been associated with increased risk of serious cardiovascular events, such as myocardial infarction or stroke. Though systematically collected data do not substantiate a connection, subjects with considerable risk for cardiovascular events will be excluded.

**Seizures:** In anecdotal reports, VCN has been associated with seizures. Potential subjects with a history of seizures will be excluded.

**Alcohol Intolerance:** In anecdotal reports, VCN has been associated with intolerance of alcohol use. Potential subjects with active alcohol abuse will be excluded.

**Sleep Disorders:** VCN use is associated with sleep disorders, including insomnia and vivid dreams. Participants will be counseled about these potential side effects and instructed to contact the investigators for any concerns.

**Gastrointestinal Symptoms:** The primary known side effect of VCN is gastrointestinal symptoms. Nausea, vomiting, and constipation are reported with VCN use.

**Risk of Multiple Study Participation:** Being in more than one research study at the same time, or even at different times, may increase the risks to you. It may also affect the results of the studies. You should not take part in more than one study without approval from the researchers involved in each study.

**Other Symptoms:** Lightheadedness has been reported with VCN use.

